- “4. Informed and privacy consent signature obtained depending on local regulations” in the ELIGIBILITY CRITERIA form [**EC. EC_IC_4**] = “Yes” OR “Not applicable: ICF waiver/Opt-out/No opposition applies”, AND
- “4. Informed and privacy consent signature obtained depending on local regulations” in the PROTOCOL DEVIATION FORM [**PDF. PDF_IC4**] is not flagged AND
- “Date of data collection (dd/mmm/yyyy)” [**PI. PI_date_coll**] is not missing.

Moreover, for patients with “4. Informed and privacy consent signature obtained depending on local regulations” in the ELIGIBILITY CRITERIA form [**EC. EC_IC_4**] = “Yes, it will be also verified that:

- “Date of informed consent form signature by the patient or by next of kin* (dd/mmm/yyyy)” [**PI. PI_date_IC**] <= “Date of data collection (dd/mmm/yyyy)” [**PI. PI_date_coll**] AND
- “Date of privacy form signature by the patient or by next of kin* (dd/mmm/yyyy)” [**PI. PI_date_priv**] <= “Date of data collection (dd/mmm/yyyy)” [**PI. PI_date_coll**]

During data elaboration this criterion will be critically reviewed and discussed, depending also on specificities of sites and countries local regulations.

Criterion 5 (UNCOMMON MUTATION COHORT). Patient harbouring uncommon or compound EGFR mutations

- “Cohort” [**PI. PI_coh_ty**] = “Uncommon Mutation cohort” AND
- “5. Patient harbouring uncommon or compound EGFR mutations” in the ELIGIBILITY CRITERIA form [**EC. EC_IC_5umc**] = “Yes” AND
- “5. Patient harbouring uncommon or compound EGFR mutations” in the PROTOCOL DEVIATION FORM [**PDF. PDF_IC5_umc**] is not flagged AND
- At least one uncommon mutation shall be present on the start date of the Index EGFR-TKI therapy (as defined in “Chapter 3”), according to the fields:
 - “EGFR mutations at start of first-line treatment” [**First-line treatment period / MUT1. MUT1_unc**]
OR
 - “EGFR mutations at start of second-line treatment” in the MUTATIONS form of the [**Second-line treatment period / MUT2. MUT2_mut_start**]

Criterion 5 (SEQUENCING COHORT). Patient with common EGFR mutations (Del19, L858R)

- “Cohort” [**PI. PI_coh_ty**] = “Sequencing cohort” AND
- “5. Patient with common EGFR mutations (Del19, L858R)” in the ELIGIBILITY CRITERIA form [**EC. EC_IC_5sc**] = “Yes” AND
- “5. Patient with common EGFR mutations (Del19, L858R)” in the PROTOCOL DEVIATION FORM [**PDF. PDF_IC5_sc**] is not flagged AND

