- from the OSIMERTINIB ADMINISTRATION DETAILS form (only for the SEQUENCING COHORT), from the field [OAD. OAD_dose] of the record with earliest non-missing start date (recorded in field [OAD. OAD_start_date]);
- from the EGFR-TKI ADMINISTRATION DETAILS form (only for the UNCOMMON MUTATION COHORT), from the field [EAD. EAD_dose] of the record with earliest non-missing start date (recorded field [EAD. EAD_start_date]). The same patient could have one or two lines of EGFR-TKI recorded in this form, and each line is identified by the field "Type of EGFR-TKI" [EAD. EAD_EGFR]: therefore, for each line recorded in this form, it will be possible to identify the starting dose with the rule defined above.

Index EGFR-TKI therapy

- *Uncommon mutation cohort*: it will correspond to the therapy recorded in the NSCLC TREATMENT form, either at [First-line treatment period] or [Second-line treatment period] depending on the following conditions:
 - [First-line treatment period] is the time point to consider if:
 - “Type of treatment” [First-line treatment period / TREAT. TREAT_ty] = “EGFR-TKI” AND
 - “Start date of this line (dd/mmm/yyyy)” [First-line treatment period / TREAT. TREAT_start_date] is lower than or equal to (“Date of data collection (dd/mmm/yyyy)” [PI. PI_date_coll] – 11.50 months) AND
 - “EGFR mutations at start of first-line treatment” [First-line treatment period / MUT1. MUT1_unc] has at least one of the options selected (excluding “Del19” and “L858R”) (*)
 - Otherwise, if the above-specified condition is not met, then the [Second-line treatment period] is the time point to consider if:
 - “Type of treatment” [Second-line treatment period / TREAT. TREAT_ty] = “EGFR-TKI” AND
 - “Start date of this line (dd/mmm/yyyy)” [Second-line treatment period / TREAT. TREAT_start_date] is lower than or equal to (“Date of data collection (dd/mmm/yyyy)” [PI. PI_date_coll] – 11.50 months) AND
 - “EGFR mutations at start of first-line treatment” [First-line treatment period / MUT1. MUT1_unc] OR “EGFR mutations at start of second-line treatment” in the MUTATIONS form of the [Second-line treatment period / MUT2. MUT2_mut_start] has at least one of the options selected (excluding “Del19” and “L858R”) (*)

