- if “Was mutational status re-evaluated at at stop of second-line treatment (or within end of observation, in case second-line treatment was not discontinued)?” [**MUT2. MUT2_reeval_stop**] = “No” OR if “Any changes in EGFR mutations with respect to start of second-line treatment?” [**MUT2. MUT2_changes_stop**] = “UNK”, patients will be classified as “Unknown EGFR mutational status”
- if “Any changes in EGFR mutations with respect to start of second-line treatment?” [**MUT2. MUT2_changes_stop**] = “No”, then the patient’s EGFR mutational status at second-line treatment stop/end of observation will be imputed as the same patient’s EGFR mutational status at second-line treatment start (as defined before)
- if “Any changes in EGFR mutations with respect to start of second-line treatment?” [**MUT2. MUT2_changes_stop**] = “Yes”, then the patient’s EGFR mutational status at second-line treatment stop/end of observation will be retrieved from the fields [**MUT2. MUT2_mut_stop**, **MUT2_mut_stop_ex20_sp**, **MUT2_mut_stop_sp**, **MUT2_concom_mut_stop**]

Acquired EGFR mutations at second-line treatment stop/end of observation

For both cohorts, the mutations found at stop of second-line treatment/end of observation (i.e. the options selected in the field [**MUT2. MUT2_mut_stop**]) will be compared to the mutations found at start of second-line treatment (i.e. the options selected in the field [**MUT2. MUT2_mut_start**]). The mutations found at second-line treatment stop/end of observation that were not present at start of second-line treatment will be classified as acquired EGFR mutations.

Classification of EGFR uncommon mutations (according to Yang's classification) for exploratory analyses

According to the MUTATIONS form, considering the EGFR mutational status at first- and second-line treatment start (but considering only lines containing EGFR-TKIs), the following definitions will be applied to classify patients' mutational status with respect to EGFR gene:

- **T790M-positive:** patients having T790M at start of either first- or second-line EGFR-TKI, but excluding patients developing acquired T790M at second-line osimertinib start;
- **Exon 20 insertion-positive:** patients having any type of exon 20 insertion at start of either first- or second-line EGFR-TKI, excluding patients included in group "a");

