- **Major uncommon mutations:** patients having either G719X and/or L861Q and/or S768I mutations at start of either first- or second-line EGFR-TKI, excluding patients included in groups "a)" or "b");
- **Others:** patients not included in groups "a)", "b)", or "c");
- **Compound mutations:** patients having more than one mutation of any type (including also common mutations).

The same patient cannot be included in more than one of the following groups, which are mutually exclusive: a), b), c), d). On the contrary, the same patient can be included in group e) and also in another group a) or b) or c) or d).

Source: Chih-Hsin Yang J, Schuler M, Popat S, Miura S, Heeke S, Park K, Märten A, Kim ES, Afatinib for the Treatment of Non-Small Cell Lung Cancer Harboring Uncommon EGFR Mutations: A Database of 693 Cases, *Journal of Thoracic Oncology* (2020), doi: <https://doi.org/10.1016/j.jtho.2019.12.126>.

Classification of EGFR uncommon mutations at first-line treatment start

The same 5 classes described above will be considered, but considering only EGFR mutational status at first-line treatment start (see algorithm described before), and without restrictions on type of treatment line.

Classification of EGFR uncommon mutations at second-line treatment start

The same 5 classes described above will be considered, but considering only EGFR mutational status at second-line treatment start (see algorithm described before), and without restrictions on type of treatment line.

In particular, "T790M-positive" group includes also patients developing acquired T790M at second-line osimertinib start, while excludes patients with T790M acquired only and treated with osimertinib. However, if the patient had also additional acquired mutations at start of second-line osimertinib (and not only acquired T790M), then the patient will not be excluded.

Only patients with Number of NSCLC treatment lines (as defined before) > 1 and [**MUT2. MUT2_reeval**] = "Yes" will be considered.

Patients without mutations at second line treatment start will not be included in "Others".

Classification of EGFR uncommon mutations at second-line treatment stop/end of observation

The same 5 classes described above will be considered, but considering only EGFR mutational status at second-line treatment stop/end of observation (see algorithm described before), and without restrictions on type of treatment line.

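### The exploratory EGFR mutation classes can be set by a mutation found at second-line start, after a first-line index TKI has already stopped

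*SAP*

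**What the plan says.** SAP section 3 (Computed variables) defines the classes for exploratory analyses as follows.

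- Time points for all classes: "considering the EGFR mutational status at first- and second-line treatment start (but considering only lines containing EGFR-TKIs").
- Class a), T790M-positive: "patients having T790M at start of either first- or second-line EGFR-TKI, but excluding patients developing acquired T790M at second-line osimertinib start".
- Class b), exon 20 insertion: "patients having any type of exon 20 insertion at start of either first- or second-line EGFR-TKI", less class a).
- Class c), major uncommon mutations: "patients having either G719X and/or L861Q and/or S768I mutations at start of either first- or second-line EGFR-TKI", less classes a) and b).
- Class d): everyone else.
- Class e), compound, which may overlap with the others: "patients having more than one mutation of any type (including also common mutations").

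None of these refers to the index therapy. The index rule in the same section tests first line before second. First line is the index if it is an EGFR-TKI, started at least 11.5 months before data collection, with an uncommon mutation at its start. Second line is reached only by the clause beginning "Otherwise, if the above-specified condition is not met, then the". Time on treatment runs from index start to index discontinuation or death, and overall survival in this cohort also runs from index start.

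Three further classifications use one time point each: first-line start, second-line start, and second-line stop or end of observation.

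**The concern.** A baseline class should be known when the clock starts. Here, for a patient whose index TKI is first line, the class can depend on a test done at the start of a second-line TKI. That test exists only for patients who have left the index TKI alive and gone on to another EGFR-TKI line. A patient still on first-line treatment cannot be moved by it, however long the response.

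Protocol section 7.1 gives the benefit of individual TKIs in individual uncommon mutations as the information needed, and section 9.5 sets out expected numbers by mutation type. If outcomes are shown by this class, part of any difference between classes could come from the definition alone.

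**Working it through.** **Tracing the rules.** Protocol section 9.5 gives no figure that depends on this definition, so there is none to reproduce. Take a patient with G719X on first-line afatinib who acquires T790M and then starts osimertinib.

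1. The patient stays eligible. Exclusion 3 in protocol section 9.2.1 removes osimertinib patients only when acquired T790M is the sole uncommon mutation.
2. The index is first-line afatinib. The primary event is the end of afatinib.
3. Class a) is closed by its exclusion, and the patient falls in class c).
4. Class e) has no such exclusion. With G719X and T790M both recorded, the patient is compound because of a test made after the primary event.

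The same route is open for T790M before a second-line TKI other than osimertinib (class a), a newly found exon 20 insertion (class b) and a newly found major mutation (class c). When the index is second line, both tests precede the clock and nothing looks ahead.

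**Comparison within the SAP.** Eligibility criterion 5 (section 2.1) is tied to the index: "At least one uncommon mutation shall be present on the start date of the Index EGFR-TKI therapy". Sites of metastases also have an index-start version in section 3. The exploratory mutation class has none.

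**Size, as an illustration with no true difference between classes.**

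Inputs from the documents: 13% compound (protocol 9.5); 6% deaths on first-line afatinib (protocol 9.12, borrowed from the sequencing cohort's setting); start at least 11.5 months before data collection (SAP 2.1).

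Assumed: every index is first line; exponential time on treatment with median 12 months; median 12 months' survival after stopping; follow-up uniform from 11.5 to 60 months; 20–50% of those who stop alive start a second-line EGFR-TKI; 10–50% of these have a new mutation recorded.

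Number moved, per 250:

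- Share still on treatment at data collection: (12/ln 2)/48.5 × (2^(−11.5/12) − 2^(−60/12)) = 0.357 × (0.515 − 0.031) = 0.173.
- Share stopped alive: 0.827 × 0.94 = 0.778.
- Compound at index start: 250 × 0.13 = 32.5; not compound: 217.5.
- Moved, low end: 217.5 × 0.778 × 0.20 × 0.10 = 3.4, giving 35.9 compound.
- Moved, high end: 217.5 × 0.778 × 0.50 × 0.50 = 42.3, giving 74.8 compound.

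Simulated Kaplan-Meier medians (400,000 patients per scenario), with classes as the SAP defines them:

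| Second-line TKI | New mutation | Compound per 250 | Median, compound | Median, non-compound | Gap (months) |
|---|---|---|---|---|---|
| 20% | 10% | 35.9 | 11.6 | 12.1 | 0.5 |
| 20% | 30% | 42.6 | 11.2 | 12.2 | 1.0 |
| 20% | 50% | 49.5 | 10.9 | 12.3 | 1.4 |
| 35% | 10% | 38.4 | 11.4 | 12.1 | 0.7 |
| 35% | 30% | 50.1 | 10.8 | 12.3 | 1.5 |
| 35% | 50% | 62.3 | 10.5 | 12.5 | 2.0 |
| 50% | 10% | 40.8 | 11.4 | 12.2 | 0.8 |
| 50% | 30% | 57.9 | 10.6 | 12.5 | 1.9 |
| 50% | 50% | 74.8 | 10.2 | 12.9 | 2.7 |

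With the class fixed at index start, the medians were 11.9–12.1 and 11.9–12.0 months, and about 17% were censored in each group. Under the SAP class, censoring fell from 15.6% to 7.4% in compound and rose from 17.5% to 21.3% in non-compound, because every patient moved is an event.

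For overall survival the class also uses information from after time zero. Patients moved must have survived to second-line start (immortal time) but must also have stopped the index TKI before data collection. These pull in opposite directions. The illustration gave 27.6 v 28.1 months at the low end and 26.3 v 28.6 at the high end. It allows no delay before second line, so it does not settle the sign in real data.

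**The case against.** **Use is not visible.** Tables 36-, 37- and 38-UNC are not split by mutation class. Tables 39- to 48-UNC appear only in the revision history (SAP section 7), and the text not shown could restrict by line or by index. Checklist item 10.4 in protocol Annex 2 says that stratified analyses are not planned. This stands: the defect is in the definition, and its effect on a reported table cannot be checked.

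**Safeguards exist.** Class a) already excludes acquired T790M at second-line osimertinib start, and protocol section 7.2 calls T790M the most common resistance mechanism. The first-line-start classification is already the right one when the index is first line. Acquired mutations are already tabulated. All of this stands and narrows the point, but none of it reaches class e).

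**The size is assumed.** Protocol section 9.5 guarantees only 50% treated with a first-line EGFR-TKI, and a second line after it is not mandatory (section 7). If half of index lines were first line, the numbers moved would halve, to 1.7–21 per 250. With 35 compound patients and an uncensored exponential with median 12 months, the half-width of a 95% interval is about 1.96 × (12/ln 2)/√35 = 5.7 months, wider than any gap above. That stands as a caution on size. The error is systematic all the same, and interval width does not excuse it.

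**Stronger readings.** A reader might infer that all the SAP's mutation classes look ahead, or that the primary result is biased. The documents support neither: three of the four classifications use a single time point, and the primary estimate pools the cohort.

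**Conclusion.** The point holds for the classification for exploratory analyses only. When the index TKI is first line, that class can be set by a finding made after the primary event, and a patient moved by switching to a second-line TKI is an event by construction. The main exposure is the compound class. Exon 20 insertions and major mutations first found at second-line start, and T790M before another second-line TKI, are lesser routes.

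The cohort-wide time on treatment (Table 36-UNC) and overall survival (Table 38-UNC) are unaffected. The spurious gap of roughly 0.5–2.7 months is illustrative: it takes every index as first line, and its rates of second-line TKI use and new mutations are not in the documents. It should not be read as an estimate of bias in this study's results. The SAP should still be corrected before any outcome is shown by this class, because the distortion is built into the definition and is cheap to remove.

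**What to change.** For any outcome analysis by mutation class, assign all classes, including compound, from EGFR mutational status at the start of the index EGFR-TKI:

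- index first line: first-line-start status only;
- index second line: status known at second-line start, using the first-line result where there was no re-test, in line with the index rule, which accepts either field.

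Name this variable in each outcome table by class. Leave mutations acquired later to the existing acquired-mutation summaries in Tables 12-UNC and 15-UNC.

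The cost is one SAP definition and its derivation code; the fields are already collected. The compound class will be smaller: about 32 of 250 from the 13% share (250 × 0.13 = 32.5), close to the 35 expected in protocol section 9.5.

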	
individual EGFR-TKIs treatment for the uncommon mutations and the overall benefit for the sequential EGFR TKI treatment with afatinib and osimertinib for the common EGFR mutations. These findings will allow for evidence-based therapy decision.
 
Uncommon mutation cohort: There is convincing data for afatinib in many uncommon mutations (L861Q, G719X, and S768I) which resulted in regulatory approval by EMA and FDA. However, uncommon mutations are very heterogeneous and more information on the benefit of individual EGFR-TKIs is needed to allow for evidence-based therapy decision.
 
Furthermore, little is known about the benefit of subsequent therapies and OS.
 
Sequencing cohort: It is still unclear which therapy sequence is the most beneficial for patients with EGFR mutated NSCLC. A recent global real-world study (GioTag) provided some insights into the outcomes of patients treated with the sequence afatinib followed by osimertinib. This study enrolled mainly Caucasian patients; study timelines and availability of drugs led to limited enrolment of long-term responders and maturity of time to treatment failure was 52% and 31% for OS. Thus, more data from Asian patients and with meanwhile longer availability of both drugs will provide more robust data with an increased maturity.
 
Various methodologies with different sensitivities can be used for mutational testing. The percentage of patients qualifying for
		

Name of company: Boehringer Ingelheim			
Name of finished medicinal product: Gi(l)otrif®			
Name of active ingredient: Afatinib (ATC code: L01XE13), gefitinib (L01XE02), erlotinib (L01XE03), osimertinib (L01XE35), Antineoplastic agents, tyrosine kinase inhibitors			
Protocol date: 31 May 2019	Study number: 1200-0316	Version/Revision: 3.0	Version/Revision date: 20 June 2020
Title of study:	UpSwing: Real World study on TKI activity in Uncommon mutations and Sequencing Giotrif®		
	the sequence afatinib followed by osimertinib patients is depending on the methodology used. Moreover, little is known about the sensitivity of the different techniques for uncommon or compound mutation. Thus, it is of interest to learn more about the methods that have been used to identify uncommon mutation (including T790M).		

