9.5 STUDY SIZE

Uncommon mutation cohort:

In LUX-Lung trials (1200.22, 1200.32, 1200.34), EAP (1200.45, 1200.55, 1200.66, 1200.193) and NIS (1200.205), 267 TKI-naïve patients were treated for uncommon mutations.

- 46% had one of the more frequent afatinib-sensitive uncommon mutation (G719X, L861Q, or S768I),
- 29% had an insertion in exon 20,
- 12% had a de novo T790M,
- 13% had a complex or compound mutation, and
- 10% had other uncommon mutations.

For the current study, a sample size of about 250 is mainly driven by feasibility. We expect that this will result in approximately

- 110 patients with frequent uncommon mutations,
- 70 patients with exon20 insertions, and
- 35 patients with compound mutations.

Given the label (and availability) for first and third generation TKIs, we assume that the majority of patients with these uncommon mutations will have been treated with afatinib. At least 50% of enrolled patients must have been treated with afatinib. At least 50% must have been treated with an EGFR-TKI in first-line (see rationale).

Comparison of the different TKIs will be limited to descriptive statistics because of the limited numbers of patients expected to have been treated with TKI other than afatinib.

Sequencing cohort:

Based on previous data from the GioTag study and expecting a higher proportion of Asian patients, the median time on treatment from start of the first-line treatment until the end of the second-line treatment is projected to be 30 months.

Table 9.5:1 shows the expected (50th percentile) width of the 95% confidence interval to be 13.7 months, with an 80% chance of observing a confidence interval of less than 16.2 months. This is based upon 200 patients with 10 percent random censoring. The width of the confidence interval would increase if the rate of censoring were higher.

Table 9.5:1 95% confidence interval width for median duration of treatment with 200 patients, 30 month underlying median duration, and increasing random censoring¹

95% CI width

	10% censoring	20% censoring	30% censoring
50 th percentile	13.7 months	15.9 months	18.8 months
80 th percentile	16.2 months	18.9 months	22.5 months

¹Calculated by simulation with 10,000 iterations

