4.2.3 Mutational Status

Table 9-SEQ. Mutations at first-line treatment (afatinib) start (ELIGIBLE PATIENTS of the Sequencing Cohort)

See corresponding table for the UNCOMMON MUTATION COHORT. However, the variable “Classification of EGFR uncommon mutations at first-line treatment start” will not be analyzed because it is not applicable for this cohort at this time point.

Table 10-SEQ. Approaches for detection of mutations at first-line treatment (afatinib) start (ELIGIBLE PATIENTS of the Sequencing Cohort) – Secondary objective #3

See corresponding table for the UNCOMMON MUTATION COHORT.

Table 11-SEQ. Mutations at second-line treatment (osimertinib) start (ELIGIBLE PATIENTS of the Sequencing Cohort)

See corresponding table for the UNCOMMON MUTATION COHORT.

Table 12-SEQ. Approaches for detection of mutations at second-line treatment (osimertinib) start (ELIGIBLE PATIENTS of the Sequencing Cohort) – Secondary objective #3

See corresponding table for the UNCOMMON MUTATION COHORT.

Table 13-SEQ. Mutations at second-line treatment (osimertinib) stop/end of observation (ELIGIBLE PATIENTS of the Sequencing Cohort)

See corresponding table for the UNCOMMON MUTATION COHORT.

Table 14-SEQ. Approaches for detection of mutations at second-line treatment (osimertinib) stop/end of observation (ELIGIBLE PATIENTS of the Sequencing Cohort)

See corresponding table for the UNCOMMON MUTATION COHORT.

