Table 13-UNC. Approaches for detection of mutations at second-line treatment start (ELIGIBLE PATIENTS of the Uncommon Mutation Cohort) – Secondary objective #3

		ELIGIBLE PATIENTS with >1 NSCLC line with re-evaluated mutational status (N=xxx)
Biologic sample(s) used for mutation testing	Tissue, Histological sample (solid biopsy)	xxx (xx.x%)
	Cytological sample	xxx (xx.x%)
	Blood (liquid biopsy)	xxx (xx.x%)
	Other (*)	xxx (xx.x%)
	UNK	xxx (xx.x%)
Methodology used for mutation testing	Amplification Refractory Mutation System (ARMS)	xxx (xx.x%)
	- ADx	xxx (xx.x%)
	- Qiagen	xxx (xx.x%)
	- Roche	xxx (xx.x%)
	- Super ARMS	xxx (xx.x%)
	- Other (*)	xxx (xx.x%)
	- UNK	xxx (xx.x%)
	ddPCR	xxx (xx.x%)
	BEAMing	xxx (xx.x%)
	Sequencing	xxx (xx.x%)
	- Sanger sequencing	xxx (xx.x%)
	- Pyrosequencing	xxx (xx.x%)
	- Other (*)	xxx (xx.x%)
	- UNK	xxx (xx.x%)
	Next-Generation Sequencing (NGS)	xxx (xx.x%)
	- Targeted NGS	xxx (xx.x%)
	- Whole-exome sequencing	xxx (xx.x%)
	- Whole-genome sequencing	xxx (xx.x%)
	- Other (*)	xxx (xx.x%)
	- UNK	xxx (xx.x%)
	Other	xxx (xx.x%)
	UNK	xxx (xx.x%)

Table 14-UNC. Summary of type of mutation detected by technique at second-line treatment start (ELIGIBLE PATIENTS of the Uncommon Mutation Cohort)

T790M-positive ELIGIBLE PATIENTS (N=xxx)	
Methodology used for mutation testing	
Amplification Refractory Mutation System (ARMS)	xxx (xx.x%)
ddPCR	xxx (xx.x%)
BEAMing	xxx (xx.x%)
...	...
Exon 20 insertion-positive ELIGIBLE PATIENTS (N=xxx)	
Methodology used for mutation testing	
Amplification Refractory Mutation System (ARMS)	xxx (xx.x%)
ddPCR	xxx (xx.x%)
BEAMing	xxx (xx.x%)
...	...
ELIGIBLE PATIENTS with Major uncommon mutations (N=xxx)	
Methodology used for mutation testing	
Amplification Refractory Mutation System (ARMS)	xxx (xx.x%)
ddPCR	xxx (xx.x%)
BEAMing	xxx (xx.x%)
...	...
Other (not included in the previous groups) ELIGIBLE PATIENTS (N=xxx)	
Methodology used for mutation testing	
Amplification Refractory Mutation System (ARMS)	xxx (xx.x%)
ddPCR	xxx (xx.x%)
BEAMing	xxx (xx.x%)
...	...

ELIGIBLE PATIENTS with Compound mutations (N=xxx)	
Methodology used for mutation testing	
Amplification Refractory Mutation System (ARMS)	xxx (xx.x%)
ddPCR	xxx (xx.x%)
BEAMing	xxx (xx.x%)
...	...

Table 15-UNC. Mutations at second-line treatment stop/end of observation (ELIGIBLE PATIENTS of the Uncommon Mutation Cohort)

ELIGIBLE PATIENTS with >1 NSCLC line (N=xxx)		
EGFR mutational status at second-line treatment stop/end of observation	Del19	xxx (xx.x%)

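### At second-line start and stop, the SAP's compound-mutation group counts an acquired T790M as the second mutation, so its rows mix acquired resistance with originally compound tumours

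*SAP*

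**What the plan says.** SAP Section 3 sets up five mutation classes. Groups a) to d) are mutually exclusive. Group e), compound, may overlap any of them and is defined as "patients having more than one mutation of any type (including also common mutations".

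Acquired T790M is dealt with only under group a). The base version takes T790M-positive patients at either line, "but excluding patients developing acquired T790M at second-line osimertinib start". For second-line start the SAP then says: "The same 5 classes described above will be considered, but considering only EGFR mutational status at second-line treatment start (see algorithm described before". The paragraph that follows again has the T790M-positive group as its subject: the group includes acquired T790M at osimertinib start, "while excludes patients with T790M acquired only and treated with osimertinib". The five classes are reused once more at second-line stop or end of observation, limited to patients re-tested at that point. Neither reuse says anything about acquired T790M in group e).

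Tables 12-UNC and 15-UNC report the classes. The layouts of Tables 14-UNC and 17-UNC tabulate test technique by class, with a panel headed "ELIGIBLE PATIENTS with Compound mutations (N=xxx". For the sequencing cohort, SAP 4.2.3 removes the classification from Table 9-SEQ, where it "will not be analyzed because it is not applicable for this cohort at this time point". Tables 11-SEQ and 13-SEQ simply refer to the corresponding uncommon-cohort tables, with no such exception.

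Protocol 9.5 describes compound mutations in TKI-naïve patients: of 267, "13% had a complex or compound mutation, and" 10% had other uncommon mutations. It expects about 35 compound cases among about 250. The protocol abstract gives the reason for interest: "little is known about the sensitivity of the different techniques for uncommon or compound mutation".

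**The concern.** A tumour that carried one EGFR mutation at diagnosis and acquired T790M under a TKI has more than one mutation at second line. Read literally, group e) then calls it compound. The first-line row in Table 9-UNC describes tumours that were compound before any TKI. The second-line rows add acquired resistance to that group under the same label, so a rise from first to second line cannot be read as a change in compound mutations.

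The sequencing cohort is selected for a common mutation followed by acquired T790M, so there the row largely restates the eligibility criteria. In Tables 14-UNC and 17-UNC, the compound panel would pool assays that found originally compound tumours with assays used to re-test for T790M.

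**Working it through.** **Inputs**
- Group e) counts mutations of any type, with no exclusion (SAP Section 3).
- Sequencing criteria 5 and 6 require Del19 or L858R at first line and T790M in the second-line-start field (SAP 2.1).
- Acquired mutations are derived by comparing the second-line list with the first-line list (SAP Section 3). This implies that the second-line field holds the full list, including the original mutation.
- Criterion 10 nevertheless foresees T790M as the only entry in that field (SAP 2.1).
- At stop, only re-tested patients are classified. If no change is recorded, the second-line-start status is carried forward (SAP Section 3).
- The planned sequencing cohort is at least 200 (Protocol 9.1).

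**The rule applied to possible records**

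| Record | Group e) as written | Acquired T790M not counted |
|---|---|---|
| Del19, then Del19 + T790M | compound | not compound |
| G719X, then G719X + T790M | compound | not compound |
| G719X + S768I, then the same + T790M | compound | compound |
| Del19, then T790M alone recorded | not compound | not compound |
| At stop: Del19 alone, T790M no longer found | not compound | not compound |

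**Sequencing cohort, second-line start (Table 11-SEQ).** All eligible patients have T790M recorded. Let q be the share whose Del19 or L858R is recorded again with it. The documents do not give q, so it is an assumption. Compound count = 200 × q:
- q = 0.5: 100
- q = 0.8: 160
- q = 0.9: 180
- q = 1: 200

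**Sequencing cohort, second-line stop (Table 13-SEQ).** Let r be the share re-tested and q the share of those with two or more mutations recorded. Both are assumptions. Compound count = 200 × r × q:
- r = 0.3, q = 1: 60 patients, 30% of the cohort but 100% of those tabulated
- r = 0.5, q = 0.8: 80 patients, 40% of the cohort and 80% of those tabulated

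**Uncommon cohort.** The protocol's expectation of about 35 is 35/250 = 14% at first line. Its source share gives 0.13 × 250 = 32.5, or 0.13 × 267 = 34.7; nothing here depends on the difference. Suppose a share p of re-tested single-mutation patients have acquired T790M recorded with the original mutation. The compound share among the re-tested is then 14% + 86% × p:
- p = 10%: 14 + 8.6 = 22.6%
- p = 50%: 14 + 43 = 57%

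SAP 4.1.3 computes Table 12-UNC percentages over all patients with more than one line. If half of them were re-tested (assumption), the same cases give 22.6/2 = 11.3% and 57/2 = 28.5%. This shows only how the row responds. The documents give no value of p for this cohort.

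**The case against.** The definition can be defended as a choice. Protocol 7.1 describes compound tumours as having more than one type of EGFR mutation, without separating de novo from acquired, and lists L858R with T790M among complex mutations. The SAP follows a published classification and reports status at each time point, when the original mutation and T790M are both present. Acquired mutations also have their own rows in Tables 12-UNC and 15-UNC. The Table 9-SEQ wording could mean that the classification was kept on purpose at later time points.

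Part of this stands. Counting acquired T790M is not wrong in itself, but the SAP should say that it is intended. Other parts of the plan keep acquired T790M apart: protocol exclusion 3, SAP criterion 10, group a), and the restriction on Table 37-UNC. Silence in group e) therefore looks like an omission. The acquired-mutation rows do not repair it. They are marginal counts, not crossed with group e), so a reader cannot subtract one from the other.

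A reader might also infer that the technique panels give a wrong answer about detection. The documents do not support that. The abstract and secondary objective 3 include T790M methods among the aims, and the first-line panel in Table 11-UNC is unaffected. The defect is that two groups are pooled. Only the layouts of Tables 14-UNC and 17-UNC are visible, so how the panels are filled is inferred from Section 3.

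**Conclusion.** The point holds as a labelling and comparability fault in descriptive mutation tables. As written, any patient whose original mutation is recorded together with acquired T790M is compound at second-line start or stop. The effect is up to 100% of the sequencing cohort in Table 11-SEQ, depending on whether the original mutation is re-recorded. In Table 13-SEQ it is limited to re-tested patients with T790M still present. In Tables 12-, 14-, 15- and 17-UNC it is an unknown share of re-tested patients.

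Four stronger readings are not supported:
- That nearly the whole sequencing cohort is mislabelled at stop: only re-tested patients are classified there.
- That every single-mutation patient with acquired T790M is affected: T790M alone is a foreseen entry and is not compound.
- That the uncommon-cohort share rises to 23–57%: the 10% has no source, the 50% is the protocol's figure for afatinib starters in the sequencing cohort (Protocol 9.9), and the denominator is not that of Table 12-UNC. Some uncommon-cohort patients also reach second line after chemotherapy, without a prior TKI.
- That main results are affected: the visible time-on-treatment, second-line failure and overall survival analyses do not use group e).

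**What to change.** At second-line start and stop, split group e) into two rows:
- (i) more than one EGFR mutation, not counting T790M acquired since first-line start;
- (ii) a single original mutation plus acquired T790M.

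Keep de novo T790M and acquired mutations other than T790M in (i). Removing every acquired mutation would be too broad, because the SAP itself treats additional acquired mutations as meaningful. Carry the split into Tables 14-UNC and 17-UNC. Drop the uncommon-mutation classification block from Tables 11-SEQ and 13-SEQ, as is already done for Table 9-SEQ.

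The cost is one extra row per table and one derived flag from fields already collected. The flag must compare with first-line status at both time points. The SAP's existing acquired-mutation variable at stop compares with second-line start and would miss T790M already present then.
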